Cover page

Title: Mitigation of radiation pneumonitis and fibrosis

ClinicalTrials.gov Identifier: NCT01754909

Most recent IRB approval Nov 13, 2017

Protocol for “Mitigation of radiation pneumonitis and fibrosis”

Cohen VA 1531-01, CLIN-004-12S

Original from Oct 31, 2012 Registration packet, incorporating amendments through July 2015

Objective

This project will test the effect of enalapril, an angiotensin-converting-enzyme inhibitor, to mitigate radiation pneumonitis and fibrosis in veterans undergoing radiation therapy for lung cancer and other cancers in the chest. It is based on the hypothesis that human normal tissue radiation injury can be safely and effectively mitigated, and on our extensive studies of radiomitigation in experimental animals. Lung cancer is more common in veterans than in the general population; this project is highly relevant to the medical care of veterans.

Research design and methodology

Enalapril or placebo will commence after the start of irradiation in veterans undergoing radiation therapy for lung cancer and other cancers in the chest, and their effects on radiation pneumonitis and fibrosis will be compared as the primary outcome measure. Enalapril will be used rather than captopril, because enalapril is given in single daily doses. This is a prospective, double-blinded, randomized, placebo-controlled trial, in a secondary-tertiary care setting. Subjects will join this trial voluntarily, based on their planned radiotherapy for lung cancer, and it is planned to enroll 200 subjects over the five years of this study. The intervention of this study is the use of enalapril or placebo, which will be maintained for the lifetime of the study subject.

2. To test the mechanism of mitigation of radiation lung injury by enalapril.
 - a. Angiotensinogen, plasma renin activity, and angiotensin II will be measured as renin-angiotensin system markers in all subjects.
 - b. The effect of enalapril on each marker will be assessed, as compared to placebo.
3. To confirm that enalapril in this use does not adversely affect cancer treatment outcomes.
 - a. Cancer recurrence and death from cancer will be compared for the enalapril and placebo groups.

These studies will be done in men and women undergoing radiation therapy for lung cancer and other cancers in the chest. Enalapril, or identical-appearing placebo, will be started within a day

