to up to 30 days of the beginning of the radiation treatments. The effect of the enalapril or placebo will be tested by their effect to reduce grade 2 or greater clinical radiation pneumonitis, by their effect on the renin-angiotensin system markers angiotensinogen, plasma renin activity, angiotensin II, and their effect to reduce radiographic evidence of pneumonitis and fibrosis.

NARRATIVE SUMMARY - HUMANS

1. **PURPOSE.** Provide the purpose or objectives of the study. Do not indicate "N/A" for this category.

To test the benefit of enalapril, an angiotensin-converting-enzyme-inhibitor, to mitigate radiation pneumonitis and fibrosis in humans.

2. **SCIENTIFIC RATIONALE.** Provide the reasons for doing the study. Do not indicate "N/A" for this category.

This project will test the effect of enalapril, an angiotensin-converting-enzyme inhibitor, to mitigate radiation pneumonitis and fibrosis in veterans undergoing radiation therapy for lung cancer and other cancers in the chest. It is based on the hypothesis that human normal tissue radiation injury can be safely and effectively mitigated, and on our extensive studies of radiomitigation in experimental animals. Lung cancer is more common in veterans than in the general population; this project is highly relevant to the medical care of veterans.

3. **BACKGROUND.** Provide information from previous studies leading up to this study, either from your laboratory or from those of others. If this is a treatment study involving investigational drugs, devices, or therapies, standard treatment must be clearly identified. Do not indicate "N/A" for this category.

Lung cancer is an important health problem for veterans. It is more common in them than in the general population, and lung cancer survival is less in veterans. Radiation therapy for lung cancer is used in over half of the cases, and it can be followed by radiation pneumonitis and fibrosis. These add significant morbidity and mortality, and they limit the doses of curative irradiation. Standard treatments for radiation pneumonitis and fibrosis are very limited. Mitigation is a new approach, being the use of an agent after initial irradiation but before the expression of radiation injury.

Our studies in rats show significant mitigation of radiation pneumonitis and fibrosis by angiotensin converting enzyme (ACE) inhibitors.

Our recent clinical trial shows the mitigation of radiation nephropathy by the ACE inhibitor captopril.

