Our retrospective clinical studies show that concurrent use of ACE inhibitors reduces the occurrence of radiation pneumonitis [and fibrosis], without lowering cancer-related survival. The safe mitigation of radiation injury has been identified as a priority by the National

Cancer Institute. We will address this critical problem. We hypothesize that the occurrence of radiation pneumonitis, fibrosis, or both in patients receiving radiation for lung cancer will be decreased by the ACE inhibitor enalapril, started after irradiation.

4. STUDY DESIGN. Provide a brief description of the design of the study (multicenter, double-blind, randomized, etc.) in narrative form. Do not provide details of specific procedures in this section (see Item 9 below). Include, as needed, a discussion of the appropriateness of research methods. Describe the statistical design and required sample size. Do not indicate "N/A" for this category.

This is a prospective, double-blinded, randomized, placebo-controlled trial, in a secondary-tertiary care setting. The ZVAMC and referring VAs in VISN 12 are the main centers; the Baltimore VAMC will be added. Subjects will join this trial voluntarily, based on their planned radiotherapy for lung cancer. We will enroll 200 subjects over the five years of this study. Statistical power analysis suggests the need for 200 subjects for the clinical endpoint, and ~ 100 subjects for the radiographic endpoint.

5. SUBJECT SELECTION AND EXCLUSION CRITERIA. Provide the specific criteria for including and excluding subjects in the study. Do not indicate "N/A" for this category.

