Cover page

Mitigation of radiation pneumonitis and fibrosis

ClinicalTrials.gov Identifier: NCT01754909

Most recent IRB approval Nov 13, 2017

Statistical methods plan

Power analysis for aim 1

For the RP endpoint, at an 11% rate of clinical RP, and an 80% mitigation effect, 97 subjects are needed per arm for type 1 error of 0.05 and a power of 0.80. The 11% and 80% figures are based on our retrospective studies. Only 49 are needed per arm for a baseline clinical RP rate of 20%. We plan for 200 subjects because there is variability in the rate of RP, and because we cannot be certain about the magnitude of efficacy of enalapril.

control	%difference	treatment	n/arm	total n
11%	50%	6%	306	612
11%	60%	4%	199	398
11%	70%	3%	136	272
11%	80%	2%	97	194
11%	90%	1%	70	140
20%	50%	10%	155	310
20%	60%	8%	101	202
20%	70%	6%	70	140
20%	80%	4%	49	98
20%	90%	2%	36	72

For a 50% radiographic rate of RP, and a halving of this by enalapril, 45 subjects are needed per arm.

50%	50%	25%	45	90
-----	-----	-----	----	----

50%	60%	20%	30	60
50%	70%	15%	21	42
50%	80%	10%	15	30
50%	90%	5%	11	22

For the radiographic fibrosis endpoint, at a 90% fibrosis rate, 29 subjects per arm would identify a 30% reduction in radiographic fibrosis at 6 or 12 months.

Endpoint and RAS analyses

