Dichotomous variables will be compared by chi-square, or Fisher's exact test, as indicated. Continuous variables will be compared by parametric or non-parametric statistics, as appropriate. Repeated measurements on the effects of enalapril and placebo on [RAS components] will be tested by a repeated measures ANOVA for continuous [RAS component] values and by a logistic type regression models [using GEE techniques for discrete [RAS component] values. In either case appropriate generalized linear models methods will be used to account for the association between repeated measurements over time on the testing procedure.] We will repeat the analysis using an appropriate regression analysis to account for possible patient factors which may influence outcome in addition to enalapril. We will also look at a model for RP and fibrosis using enalapril use and the RAS components as predictors as well as interactions between drug use and these predictors. Correlations will be made using Spearman's or Kendall correlation, as indicated. Dose modification factors (DMF) for the use of enalapril compared to placebo will not be tested since the expected radiation dose ranges will be too narrow. A more formal attempt to understand the mechanism of enalapril action on RP and fibrosis and determine if this is possibly derived through any one of the [RAS components] will use a structural equation modeling approach. This approach uses a matrix of regression coefficients from a series of regression models [of intermediate effects at the various time points to other intermediate effects at the same time point or to future intermediate or terminal effects. Using these coefficients and a postulated causal diagram which depicts which effects may be dependent on the patient history at a given time]. A final causal diagram which shows the relationship between drug, intermediate outcome and RP and or fibrosis [is constructed]. Path analysis techniques to construct the causal diagram can be constructed using the program DIGRAM (53). [This cited reference shows how this approach works by looking at causal factors for heart disease using data on behavioral factors measured at epochs in time.]

Survival analysis for aim 3

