Cancer-related survival and cancer recurrence will be compared for the enalapril and the placebo groups using Kaplan-Meier statistics. [We have calculated our ability to detect significant changes in cancer recurrence rates and in cancer survival, both for improvements in cancer-related outcomes and for adverse trends. We will be able to detect significant increases in recurrence rates or mortality. Our cohort of 162 subjects showed no difference in patient survival for those on ACE inhibitor compared to those not on ACE inhibitor. We do not

expect adverse changes in recurrence rates or patient survival. A mitigation benefit by enalapril could lead to an increase in patient survival, but less than a three month increase is not likely to be detected]

Recurrence rate change	Percent chance of detection
40 to 20 %	80%
40 to 60 %	81%

Cancer median survival change, months	Percent chance of detection
18 to 21	11%
18 to 12	60%

[There are potential pitfalls in the recurrence and survival analyses. These include the effects of interim sampling for the safety analyses, and adjustments for patient and disease characteristics as well as missing data.] The interim masked safety analyses will use the O'Brien correction to take into account the multiple analyses. In our analysis of survival, we will compare the recurrence-free survival rates between the treatment arms of the study in two ways. First we will examine the rates of death or recurrence using a Cox model. In this model we will adjust for patient/disease characteristics such as site of treatment, gender, age, stage of disease at randomization, and radiation dosage. We will also compare the disease free survival probabilities at two years using techniques that we have published (52). This method allows us to deal with the partial information available in patients who do not have a potential follow-up time of two years. This approach, which is a censored data version of logistic regression, will allow us to adjust the comparisons for patient, disease, and treatment factors. We picked two years here since the empirical evidence is that the disease-free survival curves tend to flatten out at around 20 months.

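### Clinical radiation pneumonitis is tested as a crude proportion, with no assessment window and no rule for deaths or short follow-up, so the RP rate is hard to interpret and the planned power is optimistic

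*SAP*

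**What the plan says.** The Protocol's design paragraph says of enalapril and placebo that "their effects on radiation pneumonitis and fibrosis will be compared as the primary outcome measure". The clinical part is then specified as "their effect to reduce grade 2 or greater clinical radiation pneumonitis".

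The SAP (Power analysis for aim 1) treats clinical RP as two fixed proportions: "at an 11% rate of clinical RP, and an 80% mitigation effect, 97 subjects are needed per arm for type 1 error of 0.05", with 80% power. It attributes the 11% and the 80% to the team's retrospective studies. The SAP (Endpoint and RAS analyses) gives the test: "Dichotomous variables will be compared by chi-square", with Fisher's exact test as the alternative. A second analysis is promised: "We will repeat the analysis using an appropriate regression analysis to account for possible patient factors which may influence outcome in addition to enalapril". That sentence covers patient factors; it does not mention time at risk, censoring or death.

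On follow-up, Protocol section 4 states: "We will enroll 200 subjects over the five years of this study". The SAP's survival power table for aim 3 starts from a median of 18 months. For aim 3, and only there, the SAP names Kaplan-Meier, a Cox model and a censored-data form of logistic regression for subjects with incomplete follow-up. The one time point attached to an aim 1 endpoint is 6 or 12 months, for radiographic fibrosis.

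**The concern.** A yes/no comparison needs everyone to be observed over the same period, or a rule for those who are not. Neither appears for clinical RP. On the plain reading, a subject who dies at month 2, or who enrols shortly before the analysis, stays in the denominator as free of RP.

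Two things follow. First, the observed RP rate is lower than the rate that would be seen with complete follow-up, by an amount that depends on survival and calendar time. It is then hard to interpret, and the power is lower than planned. Second, if survival differs between arms, time at risk differs too, and the crude proportions move apart even when enalapril has no effect on RP. The SAP raises that possibility itself: "A mitigation benefit by enalapril could lead to an increase in patient survival".

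**Working it through.** **1. The plan's own figure.** With p1 = 0.11, p2 = 0.11 × 0.20 = 0.022 and mean p̄ = 0.066:

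n = [zα√(2p̄(1−p̄)) + zβ√(p1(1−p1) + p2(1−p2))]² / (p1−p2)²

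At one-sided 0.05 (zα = 1.645, zβ = 0.842) this is 97.4, which matches the SAP's 97. At two-sided 0.05 it is 123.8, that is 124. The stated 80% power is therefore a one-sided figure, although the SAP does not say so. By exact binomial enumeration, two-sided chi-square power at 100 per arm for 11% vs 2.2% is 74%. That is the baseline used below.

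**2. How much follow-up is missing.** Inputs from the documents are the 18-month median (SAP, aim 3) and accrual over 60 months (Protocol section 4). Assumed: exponential survival, uniform accrual, analysis at month 60, 1:1 allocation.

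| Month t | Dead by t: 1 − 0.5^(t/18) | Potential follow-up below t: t/60 |
|---|---|---|
| 3 | 11% | 5% |
| 6 | 21% | 10% |
| 12 | 37% | 20% |

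**3. Share of RP events that would be observed.** The documents give no onset distribution, so two are shown: uniform over months 1-6 and over months 1-12. RP and death are taken as independent. The share f is the mean over onset times t of 0.5^(t/18) × (1 − t/60).

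- Late accrual alone: 1 − 3.5/60 = 0.942 (months 1-6); 1 − 6.5/60 = 0.892 (months 1-12).
- Deaths alone: 0.875; 0.784.
- Both together: 0.825; 0.704.

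**4. Rates and power, 100 per arm, two-sided chi-square, exact.**

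| Scenario | Onset | Control vs enalapril | Power |
|---|---|---|---|
| No deaths, full follow-up | any | 11% vs 2.2% | 74% |
| Deaths and late accrual | 1-6 | 9.1% vs 1.8% | 64% |
| Deaths and late accrual | 1-12 | 7.7% vs 1.5% | 55% |
| 11% already net of deaths; late accrual only | 1-6 | 10.4% vs 2.1% | 71% |
| 11% already net of deaths; late accrual only | 1-12 | 9.8% vs 2.0% | 68% |

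With 12 further months of follow-up after accrual, only the deaths remain, and power is 67% (months 1-6) or 61% (months 1-12). On the plan's implicit one-sided basis (normal approximation), power falls from 81% to 73% or 67% when both deaths and late accrual apply.

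**5. Does the comparison itself go wrong?** With the same f in both arms, the relative risk is unchanged (0.022f / 0.11f = 0.20). Under no RP effect, the simulated type I error is 4.9%. With no RP effect and unequal survival, the false relative risk is the ratio of the two f values:

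| Median survival, months | Onset 1-6 | Onset 1-12 |
|---|---|---|
| 18 vs 12 | 0.774/0.825 = 0.94 | 0.630/0.704 = 0.89 |
| 18 vs 21 | 0.841/0.825 = 1.02 | 0.728/0.704 = 1.03 |

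Exact rejection rates in these four cases lie between 5.2% and 5.6%.

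**6. What a time-to-event test changes.** In 4,000 simulated trials per scenario, a cause-specific log-rank test had power 66% against 63% for chi-square (onset months 1-6) and 57% against 54% (months 1-12). With 18 vs 12 months and no RP effect, it rejected in 4.8% and 5.0% of trials, against 5.6% and 5.7% for chi-square.

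**The case against.** The strongest reply is that most of the lost power has nothing to do with the choice of test. Events that are prevented by death or fall after the analysis date are missing under any method, and the log-rank test regains only 2-3 points. This stands: the remainder is a matter of sample size and length of follow-up.

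Second, a reader might infer that the chi-square test is invalid, or that a drug which shortened life would be declared protective. The documents do not support that. Randomisation balances administrative follow-up, and equal mortality leaves relative risk and type I error alone. The SAP expects no adverse change in survival and cites a cohort of 162 subjects that showed no difference. The only difference it foresees is a benefit, which would count slightly against enalapril. Even 18 vs 12 months gives a false reduction of 6% or 11%, the larger only if onset is spread over a year, and rejection stays below 6%. Aim 3 also examines survival directly.

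Third, the 11% is retrospective and may already include deaths. The plan does not say that RP follow-up stops at year five, and the detailed aim 1 text is not among the pages supplied, so a window could be stated elsewhere. These points reduce the size of the problem and limit the claim to the text available. They do not supply the missing rule.

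**Conclusion.** The point holds as a gap in the specification with a moderate cost. In the text supplied, a primary endpoint is compared as a crude proportion without a window, a minimum follow-up or a rule for deaths, while the same SAP handles partial follow-up for aim 3.

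The main consequence is an RP rate that is hard to interpret and a loss of two-sided power: about 10 to 19 points (74% to 64% or 55%) if 11% is free of deaths, or about 3 to 6 points (to 71% or 68%) if it is not. Bias between arms arises only with unequal survival and is modest in the survival scenarios of the SAP's own table (relative risk 0.89-0.94 or 1.02-1.03).

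These figures rest on analysis at month 60, uniform accrual, exponential survival, RP independent of death, and assumed onset windows. The 18 months is a planning value, not an observed trial median. The change is worth making, but the results do not show that the stated test would give a false conclusion.

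**What to change.** - **Clinical RP.** Analyse time from randomisation to first grade 2 or higher RP with a cause-specific log-rank test and Cox model, censoring at death and at end of follow-up. Stratify by cancer stage, the randomisation stratum in Protocol section 9. Report cumulative incidence at 6 and 12 months by arm with death as a competing event. Keep chi-square or Fisher's exact test as supportive.
- **Radiographic RP.** Protocol section 9 leaves imaging to periodic regular care, so onset is known only to lie between scans. Use cumulative incidence at fixed imaging times or an interval-censored method, not an ordinary log-rank test.
- **Power.** Qualify the stated power for deaths and short follow-up, and say whether the 11% already includes early deaths. The new analysis will not recover most of the loss.

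The cost is SAP wording, slightly less simple reporting, and recording of RP onset dates. The Protocol describes prospective tracking of complications by a coordinator (section 10) and monthly chart reviews (section 12), so dates should be obtainable, but it does not say that they are collected.

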The study drug, enalapril or placebo, will be in addition to usual clinical care of subjects undergoing radiation therapy for lung cancer. Enalapril, or placebo, will be given orally, started within a day to up to 30 days of the beginning of the radiation treatments. They will be enrolled at the start of radiation therapy (RT), stratified for cancer stage, then randomized to enalapril or identical-appearing placebo. Randomization will be done by the Department of Biostatistics, Medical College of Wisconsin, using random number tables; the center pharmacies will be notified of the assignment to enalapril or placebo. There will be no stratification by age, gender, lung cancer histology, or use of chemotherapy since these do not have a consistent relation with the occurrence of RP. There is no stratification by center. Study drug is obtained from Expert Pharmacy Inc, with identical appearing enalapril and placebo tablets. It is held in the VA research pharmacy at Milwaukee, in a restricted access area under the aegis of the research pharmacist. It will be sent to patients at the Baltimore site upon their enrollment. The study drug dose will be

2.5 mg to start, and will be increased in increments of 2.5 mg to 10 mg per day, as tolerated. Clinical follow up of study subjects will be identical to that of subjects undergoing radiation therapy for lung cancer but who are not participating in this study, with the addition of four blood samples. One blood sample one week after starting the study will be to check for adverse effects of the study drug. Three more blood samples will be obtained for renin-angiotensin system (RAS) assays, done on three blood samples from each subject, at the start of the study, at 3 weeks after the start, and at the end of radiation therapy. Each of these four research-related blood samples will be approximately one teaspoon of blood obtained by venipuncture. Compliance is assessed by monitoring the requests for study drug refills. It will be verified at the end of the study by the elevation in plasma renin in subjects on enalapril compared to those on placebo. Study subjects will be monitored for adverse effects of study drug. The development, or not, of radiation pneumonitis and fibrosis will be assessed in the study subjects, as part of ongoing regular care, as are the periodic radiographic imaging and lung function testing. Quality of life will also be assessed.

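### The RAS marker test is not adjusted for the start-of-study value and its drug term is not named, which on the natural reading costs precision in aim 2

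*SAP*

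**What the plan says.** Aim 2b in the Protocol (Research design and methodology) is a between-arm question: "The effect of enalapril on each marker will be assessed, as compared to placebo". Protocol item 9 (Procedures) schedules three RAS samples per subject, "at the start of the study, at 3 weeks after the start, and at the end of radiation therapy".

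The SAP (Endpoint and RAS analyses) states that repeated measurements of a marker "will be tested by a repeated measures ANOVA for continuous [RAS component] values", with logistic-type GEE models for discrete values. It adds that generalized linear models "methods will be used to account for the association between repeated measurements over time". Three things are left open:

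- whether the start-of-study sample is an outcome or a covariate;
- whether the drug is tested by the arm main effect or by arm-by-time;
- whether the first sample is drawn before the first dose.

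Two other sentences in that section come near the subject. One promises a repeat analysis: "We will repeat the analysis using an appropriate regression analysis to account for possible patient factors which may influence outcome in addition to enalapril". The other describes a path model that relates intermediate effects "to other intermediate effects at the same time point or to future intermediate or terminal effects".

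**The concern.** If the start-of-study sample is drawn before any study drug, it carries no drug effect. It is useful because it predicts a subject's later values, and a covariate uses that information. An ordinary repeated-measures ANOVA over all three times does not. Its arm main effect averages one null difference with two active ones. Its arm-by-time term works on raw change, which subtracts the whole baseline value rather than the part that predicts the later value.

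At stake is the precision of the aim 2 comparison for each marker. Protocol item 9 also relies on the arm difference in plasma renin to verify compliance, so that comparison serves two purposes. Leaving the tested term open also means that the estimand for aim 2 is not fixed in advance.

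**Working it through.** **The plan's own figure.** There is none to reproduce. The SAP gives no sample size, power, standard deviation or correlation for aim 2.

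**Inputs.** Three samples per subject come from Protocol item 9. The total of 200 comes from Protocol item 4 ("We will enroll 200 subjects over the five years of this study"). The rest is assumed:

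- equal variance σ² at each time;
- one common correlation r between any two samples, taken as 0.3, 0.5 and 0.7;
- no arm difference at the first sample;
- the same difference d at both later samples.

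The power illustration also assumes 100 per arm and a two-sided 0.05 level.

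**Three estimators of d.** Let B be the baseline and P the mean of the two later samples. Then Var(B) = σ², Var(P) = σ²(1+r)/2 and Cov(P,B) = rσ². Variances per arm, in units of σ²:

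- Baseline-adjusted, P − rB: (1+r)/2 − r²
- Post-minus-baseline contrast (1 df), P − B: (1+r)/2 + 1 − 2r
- Arm main effect over three times. Its expected difference is 2d/3, so it is rescaled by 3/2, giving P + 0.5B: [(1+2r)/3] / (2/3)²

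| r | Adjusted | Change | Main effect |
|---|---|---|---|
| 0.3 | 0.65 − 0.09 = 0.56 | 0.65 + 1 − 0.6 = 1.05 | (1.6/3)/(4/9) = 1.20 |
| 0.5 | 0.75 − 0.25 = 0.50 | 0.75 + 1 − 1.0 = 0.75 | (2.0/3)/(4/9) = 1.50 |
| 0.7 | 0.85 − 0.49 = 0.36 | 0.85 + 1 − 1.4 = 0.45 | (2.4/3)/(4/9) = 1.80 |

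**Sample-size factors.** For fixed d and power, the number of subjects is proportional to the variance.

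- Change against adjusted: 1.05/0.56 = 1.875; 0.75/0.50 = 1.50; 0.45/0.36 = 1.25.
- Main effect against adjusted: 1.20/0.56 = 2.1; 1.50/0.50 = 3.0; 1.80/0.36 = 5.0.

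**In power terms.** Take the effect that the adjusted analysis detects with 80% power at 100 per arm: 0.296, 0.280 and 0.238 SD at r = 0.3, 0.5 and 0.7. Power for the alternatives is then:

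| Test | r = 0.3 | r = 0.5 | r = 0.7 |
|---|---|---|---|
| 1-df change contrast | 53% | 63% | 71% |
| 2-df arm-by-time test | 43% | 52% | 61% |
| Three-time main effect | 48% | 37% | 24% |

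The 2-df row is the usual interaction test with three times.

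**Direction.** All three estimators have the form P − bB, with b = 1 for change and b = −0.5 for the main effect. Adjustment uses the b that minimises the variance. In large samples it therefore cannot do worse than either, whatever the correlation.

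**Timing.** Protocol item 9 enrols subjects when radiotherapy starts but lets study drug begin up to 30 days later. Three weeks is 21 days. If the sampling clock runs from enrolment, some 3-week samples could precede the first dose. The one-week sample that checks for study-drug adverse effects suggests that study start means drug start, but the text does not say so.

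**The case against.** The strongest objection is that the fault is partly inferred. A reader might infer that the SAP expressly makes the baseline an outcome. It does not: it is silent on the sample's role, and all three samples as outcomes is only the natural reading. The supportable statement is that adjustment and the tested term are not specified.

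A reader might also infer that most of aim 2's precision is lost. The documents do not support that. The factors of 2.1 to 5.0 apply only if the arm main effect is the test, and arm-by-time is at least as natural with a baseline in the series. For the 1-df contrast at r = 0.7 the factor is 1.25. Nothing in the documents shows that precision is limiting for aim 2 with 200 subjects.

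Nor do the documents show that subjects with a missing sample would be dropped. Classical repeated-measures ANOVA does this, but the generalized linear models wording leaves room for a model that does not. Keeping the baseline in the outcome vector is not wasteful in itself either: a longitudinal model with a common baseline mean across arms matches covariate adjustment. Finally, the planned test is not biased, because randomisation protects it.

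These points limit the finding but do not remove it. The generalized linear models sentence deals with correlation over time, not baseline adjustment. The repeat regression could include the baseline marker, but its patient factors are unnamed, whereas the SAP's Cox model for aim 3 lists its covariates. The path model does relate earlier to later values, but it addresses mechanism rather than the aim 2b comparison.

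**Conclusion.** The point holds as a free improvement to a non-primary aim. The SAP specifies neither baseline adjustment nor the term that tests enalapril, and no other sentence supplies them. The direction of the loss is firm on the natural reading. Its size is not, because it depends on r and on the tested term, and the documents give neither. Over r = 0.3 to 0.7 the sample-size factor runs from 1.875 down to 1.25 for the 1-df contrast, and from 2.1 up to 5.0 if the main effect were used. These figures rest on equal variances, a common correlation, a truly pre-dose first sample and equal effects at both later samples. The last two are uncertain given stepwise dose increases and the window for starting study drug. The consequence is lost efficiency and an undefined contrast, not an invalid test.

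**What to change.** In the SAP, replace the repeated-measures ANOVA sentence with a mixed model for the 3-week and end-of-radiotherapy values. Its fixed effects would be the start-of-study marker value (on the log scale if skewed), treatment, time, treatment-by-time and the stratification factor, stage. A longitudinal model of all three samples with a common baseline mean across arms is an equivalent choice. In addition:

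- name the treatment contrast that answers aim 2b, for example the average over the two later samples or the difference at one named time;
- use the same baseline covariate in the GEE models for discrete values;
- state that the start-of-study sample is drawn before the first dose, and reconcile the sampling clock with the 30-day window for starting study drug in Protocol item 9.

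The cost is a few sentences of SAP text and a clarification in Protocol item 9. The three samples are already scheduled, so no new data are needed.

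### Does the drug-by-RAS interaction model need a sparse-data method and a fixed sampling time written into the SAP?

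*SAP*

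**What the plan says.** The aim 2 section of the protocol states: "Angiotensinogen, plasma renin activity, and angiotensin II will be measured as renin-angiotensin system markers in all subjects". Protocol section 9 (Procedures) has blood drawn for these assays "at the start of the study, at 3 weeks after the start, and at the end of radiation therapy", and it expects "the elevation in plasma renin in subjects on enalapril compared to those on placebo" to confirm compliance.

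The SAP, under Endpoint and RAS analyses, first plans the between-arm comparisons and repeated-measures models for the markers. It then adds a model for RP and fibrosis "using enalapril use and the RAS components as predictors as well as interactions between drug use and these predictors". For this model it gives no estimator, no joint test, no significance level, no rule for sparse events, and no choice among the three sampling times. The language is that of an additional look at the data. The structural equation and path analysis that follows is presented as the more formal study of mechanism.

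The event rates come from the SAP's Power analysis for aim 1. The lead case is set "at an 11% rate of clinical RP, and an 80% mitigation effect". The planned 200 subjects are justified partly because "there is variability in the rate of RP". The radiographic case is introduced with "For a 50% radiographic rate of RP, and a halving of this by enalapril", and protocol section 4 puts the need at about "100 subjects for the radiographic endpoint".

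**The concern.** A logistic model with a drug term, three markers and three interactions needs information on the marker slopes within each arm. If enalapril works as well as the SAP's lead case supposes, very few subjects on enalapril will develop clinical RP. The interaction terms would then rest on about two events. The better the drug works, the less this model can be estimated.

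Two things could go wrong. The maximum-likelihood fit may not exist, because the markers separate events from non-events perfectly within an arm. Or a p-value may be taken from such a fit and read as evidence that the drug acts through the renin-angiotensin system. A false mechanistic claim under aim 2 would be the cost. Using all three sampling times would make matters worse, at 1 + 9 + 9 = 19 slopes.

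**Working it through.** **Inputs.** Rates of 11% and 11% × (1 − 0.80) = 2.2%, type 1 error 0.05, power 0.80 and 200 subjects (SAP, Power analysis for aim 1). Three markers (protocol, aim 2). Assumed: 100 per arm, one value per marker, independent standard-normal markers unrelated to RP, and maximum-likelihood logistic regression. The documents give no marker distributions.

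**The plan's own figure.** The SAP gives 97 per arm for 11% against 2.2%. The usual two-proportion formula with one-sided 0.05 gives 96 (unpooled variance) or 98 (pooled variance). Two-sided 0.05 with pooled variance gives 124. The 97 is therefore consistent with a one-sided calculation, and the rates are being read as the SAP intends.

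**Events and slopes.** Expected events: 100 × 0.11 + 100 × 0.022 = 11 + 2.2 = 13.2. Slopes: 1 + 3 + 3 = 7. Events per slope: 13.2 / 7 ≈ 1.9.

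**Share with no finite fit.** The fully interacted model factorises by arm, so the enalapril arm decides. With events there Binomial(100, 0.022), P(0) = 0.108, P(1) = 0.243 and P(2) = 0.271. The simulated chance of no finite fit is 1 with no events, about 0.23 with one and about 0.013 with two:

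0.108 + 0.243 × 0.23 + 0.271 × 0.013 ≈ 0.167.

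Direct simulation gave 16.3% in 15,000 trials and 17.1% in 10,000.

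**Where the 10% comes from.** In the 10,000-trial run the joint 3-df likelihood-ratio test rejected in 34.7% of non-finite fits and 5.5% of finite fits:

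0.171 × 0.347 + 0.829 × 0.055 = 0.059 + 0.046 = 0.105.

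Trials with no enalapril event, about 11% of all trials and most of the non-finite ones, never reject. Trials with exactly one event supply 0.243 × 0.233 = 5.7 of the 10.5 points.

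**The same null with other tests** (11% against 2.2%, ranges over separate runs):

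| Joint interaction test | Rejection rate |
|---|---|
| Likelihood ratio, non-finite fits counted | 9.4 to 10.8% |
| Likelihood ratio, finite fits only | about 5.5% |
| Score | 4.2 to 5.1% |
| Wald | about 1% |
| Firth penalised likelihood ratio | 2.0 to 2.9% |

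**Markers shifted by the drug.** Because plasma renin is expected to rise on enalapril, the run was repeated with markers correlated at 0.5 and shifted by drug. A shift of 1 SD gave 16.4% non-finite and 10.8% likelihood-ratio rejection; 2 SD gave 16.6% and 9.7%. The picture does not change.

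**Other SAP rates** (100 per arm, likelihood ratio with all fits counted). Of the ten clinical rows, four give 9.2 to 10.9% and six give 6.0 to 8.5%. Radiographic RP at 50% against 25% gives 5.7% with 200 subjects and 6.8% with 100, with no non-finite fits. Fibrosis at 90% against 63% gives 6.2%.

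**What a prescribed method would gain.** For an enalapril-arm odds ratio of 3 per SD, Firth power is 11% at 11% against 2.2% and 23% at 20% against 4%. In a run that compared the two, a score test reached 15% against 11% for Firth at the first pair of rates, and 30% against 25% at the second.

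**The case for a change.** The strongest case for a change is that the sparse scenario is the sponsor's own lead assumption, drawn from its retrospective studies, and that the error rate of the interaction test runs from about 1% to about 10% depending on choices left open. At that assumption, a trial with a single enalapril event rejects in 23% of cases by likelihood ratio. Dropping the failed fits brings the rate back to about 5.5%, but then about one trial in six has no result. Writing down an exploratory label, one value per marker and a penalised fit would cost only SAP wording.

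The event arithmetic and the 16 to 17% stand, and so does the observation that the estimator and sampling time are not written down. What does not stand is the step to a faulty plan. The 10% needs an analyst to test three interactions on one or two events in an arm, obtain a fit that has not converged, and report its likelihood-ratio p-value regardless. The SAP asks for none of this. It states no significance level for this model either, so there is no intended rate that is being doubled.

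The remedy is also open to dispute. Firth is conservative here, and the score test had size closer to 5% and more power. One value per marker sets aside repeated measurements that the protocol collects on purpose. No estimator makes up for having about two events on enalapril.

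**Conclusion.** No change to the plan is needed. At 11% against 2.2% with 100 per arm, the clinical RP version of this model would be badly underpowered, and about one time in six it would have no finite maximum-likelihood fit. The excess of false positives, about 10% against 5%, arises only for a likelihood-ratio test that counts the failed fits, and that test is assumed rather than planned. Statistical software would normally show the separation, and a competent analyst would then use a score or penalised test, reduce the model, or report that it could not be estimated.

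The primary RP comparison, the between-arm marker comparisons and the path model do not depend on this model. The problem is milder at six of the ten clinical rows and nearly absent for radiographic RP. What is left is missing detail in a side analysis, together with a fair trade-off between conservatism, power and use of the repeated samples.

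The sizes rest on equal arms of 100, one value per marker, and null markers that are independent and normal, or correlated and shifted by drug. With all three sampling times the model would be sparser still, and the same judgement would apply.
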